Title	A first in man, prospective, open-label, single arm, multicenter clinical investigation to assess the safety and performance of the ARGOS-SC suprachoroidal pressure sensor system in patients with glaucoma undergoing non-penetrating glaucoma surgery
Study Number	ARGOS-SC01
Sponsor	Implandata Ophthalmic Products GmbH
Name of IMD	ARGOS-SC System The ARGOS-SC system is a non-CE marked investigational medical device composed of the implant and its accessories: Implant: ARGOS-SC pressure sensor implant for suprachoroidal placement Accessories: MESOGRAPH reading device, telemetric Multiline Connector
Intended use	The sensor device is intended to be permanently implanted in the human eye and used in conjunction with the hand-held MESOGRAPH reading device to telemetrically measure the intraocular pressure (IOP) of the implanted eye.
Indication for use	Patients with glaucoma and scheduled for non-penetrating glaucoma surgery
Study Purpose	The purpose of this study is to evaluate both the safety and feasibility of the surgical implantation of the ARGOS-SC implant during non-penetrating glaucoma surgery and the safety and usability of the ARGOS-SC implant and system in the year following the implantation.
Study Design	This study is designed as a prospective, open-label, multicenter, single-arm clinical investigation. Subjects will be followed up at regular intervals for one year following implantation to collect safety and performance information. Enrollment will be halted at every serious adverse device event (SADE).
Sample Size Considerations	The sample size calculation was based on the study's dual purpose of establishing safety and comparability of IOP measurements with the ARGOS-SC system to those made with GAT and DCT. IOP measurements will be made with all devices at various time points, resulting in a within individual control for IOP variables. Based on these calculations (performance, safety) and considering possible drop-outs, the exploratory investigation will enroll 24 patients. The minimum number of measurements required to hold the performance claim is approx. 120. With multiple (>8) measurements with either method (ARGOS, GAT) per patient, a sufficient number of paired measurements (in total >>120 measurement pairs) will be available to show equivalence of the methods (primary objective)[2].

Page 7 of 97

Patients with glaucoma who are scheduled to undergo non-penetrating glaucoma surgery.
Primary ObjectivePerformanceTo evaluate the limits of agreement between measurements with Goldmann Applanation Tonometry (GAT), Pascal Dynamic Contour Tonometry (DCT) and the ARGOS-SC system in the 12 months following implantationSecondary Objectives SafetyTo evaluate the safety and tolerability the ARGOS-SC pressure during implantation and throughout a 12 months follow-up period.Performance To evaluate the performance of the ARGOS-SC system up to 12 months after implantation
 Inclusion Criteria Eligible subjects must meet all the following inclusion criteria: Subjects able to understand the informed consent and willing to participate as evidenced by providing informed consent. Patients aged ≥ 18 on the day screening Female subjects of childbearing potential (not surgically sterilized or more than one year post-menopausal) must have a negative pregnancy test (urine beta-hCG) within 24 hours prior to ARGOS-SC pressure sensor implantation. Diagnosis of open angle glaucoma requiring a non-penetrating glaucoma surgery (NPGS). The medical indication for a non-penetrating glaucoma surgery must be given irrespective of the study participation. Potential study patients will be solicited for participation in the clinical trial only after the patient has given consent to the non-penetrating glaucoma operation. Subjects able and willing to attend all scheduled visits and comply with all study procedures.
1. Contraindications for a non-penetrating glaucoma surgery

Page 8 of 97

 Neovascular glaucoma, primary and secondary angle closure glaucoma
Condition after previous glaucoma incisional surgery
• IOP > 40 mmHg
2. Myopia (> -6 dpt) or hypermetropia (> +4 dpt)
 Axis length < 22 mm or > 26 mm Detient with single que vision (mon evision)
4. Patient with single eye vision (monovision)
degeneration 30 days prior to inclusion, or macular edema
6. Acute retinal detachment
Uncontrolled Diabetes Mellitus (DM) with manifestation of moderate to severe non-proliferative diabetic Retinopathy (DR) or proliferative DR.
8. History or evidence of severe active inflammatory eye diseases (i.e. uveitis, retinitis, scleritis) in one or both eyes within 6 months prior to ARGOS-SC implantation
 Ocular surgery procedure(s) (excluding selective laser trabeculoplasty and peripheral iridotomy) within 6 months (cataract surgery within 3 months) prior to ARGOS-SC implantation in the study eye that can affect the assessment of IOP by Goldmann Applanation tonometry
 Ocular disease other than glaucoma that may affect assessment of visual acuity and/or IOP by Goldmann Applanation tonometry/Pascal Dynamic Contour Tonometry (e.g. choroidal hemorrhage or detachment, lens subluxation, thyroid ophthalmopathy)
11. Existence of other active medical eye implant and/or other active medical implants in the head/neck region
12. Difficulties or complications during NPGS procedure or implantation of ARGOS-SC sensor, as assessed by surgeon (e.g. perforation of trabeculo- descement's membrane; excessive aqueous filtration through TDM leading to shallow anterior chamber; excessive bleeding; choroidal detachment)
13. Severe generalized disease resulting in a life expectancy shorter than a year
14. Currently pregnant or breastfeeding
15. Participation in any study involving an investigational drug or device within the past 30 days or ongoing participation in a study with an investigational drug or device
16. Patients who are not suitable for the study based on the surgeon's evaluation (e.g. patients affected by Parkinson's disease or essential tremor)
17. Patients unable or unwilling to understand or comply with required study procedures
18. Patients with psychiatric disorders influencing their judgement or autonomy

Page 9 of 97

Study	Screening (SC)
Procedures	Consecutive potential subjects will undergo informed consent process up to 28 days prior to surgery. Consenting subjects will be screened. Screening visit will includes
	Demographics
	Medical history
	 Pregnancy tests for females of child-bearing potential
	General
	 Vision-related Quality of Life (VQoL) questionnaire
	Visual acuity (ETDRS)
	Perimetry
	Concomitant medication
	External eye photography
	Anterior segment
	Optical coherence tomography (OCT) of cornea and anterior chamber
	Slit lamp biomicroscopy
	Gonioscopy
	Posterior segment
	Slit lamp biomicroscopy
	Optical coherence tomography (OCT) of macula and optic nerve
	Fundus photography
	IOP measurements
	Goldmann Applanation tonometry (GAT)
	Pascal Dynamic Contour Tonometry (DCT) (if available)
	Surgery (V01)
	On day of surgery or one day prior to surgery, subjects will again be assessed for
	eligibility requirements including pregnancy testing for females of childbearing
	potential. Subjects who continue to meet eligibility requirements will undergo
	non-penetrating glaucoma surgery with ARGOS-SC pressure sensor implantation

Page 10 of 97

and standard clinical procedures. If it becomes apparent during the surgery that the subject is not a suitable candidate for the ARGOS-SC pressure sensor implant, the subject will be removed from the study and returned to standard of care.

At Visit 01, data will be collected regarding:

General

- Implantation procedure questionnaire (surgeon)
- AE/ADE/SAE/SADE/UADE
- Concomitant medication
- Device deficiency

Follow-up (V02 to V09)

The follow-up period after surgery will consist of 8 visits (Day 1 until Day 360). The examinations performed at each visit are listed without mentioning the single visit in parentheses. Examinations that are carried out only at distinct visits are indicated in parentheses. The follow-up visits will include:

General

- VQoL questionnaire (V06, V07, V09)
- Visual acuity (EDTRS)
- Perimetry (V06, V07, V09)
- External Eye Photography (V04-V09)
- Heidelberg Engineering ANTERION[®] (location of ARGOS-SC)(V04-V09), if available
- User acceptance questionnaire (investigator) (V09)
- User acceptance questionnaire (patient) (V09)
- AE/ADE/SAE/SADE/UADE
- Concomitant medication
- Device deficiency

Anterior Segment

- Slit-lamp biomicroscopy
- Optical coherence tomography (OCT) of cornea and anterior chamber (V04-V06)
- Gonioscopy (V06, V07, V09)

Posterior segment

• Slit lamp biomicroscopy

	 Optical coherence tomography (OCT) of macula and optic nerve (V06, V07, V09)
	 Fundus photography (V06, V07, V09)
	IOP measurements
	• GAT
	 Pascal DCT (V05-V09) (if available)
	ARGOS-SC system measurements
	 Optional: 24-hours measurements inpatient with ARGOS-SC and GAT (V06, V07, V09)
	ARGOS-SC system self-measurement at home
Data Analysis	Primary Endpoint
and Statistics	Performance
	- Level of Agreement between measurements made using GAT, Pascal DCT and the ARGOS-SC system from V02 (day 1) through V09 (day 360).
	Secondary Endpoints
	Safety
	 Number of patients experiencing a device-related SAE (SADE) at any time during implantation and in the first 12 months (Day 0 to Day 360) following it
	 Incidence, nature, severity and seriousness of observed adverse events and adverse device events at any time during implantation and in the 12 months following it
	Performance
	- Repeatability of the ARGOS-SC measurement
	 Incidence, nature and seriousness of observed device malfunctions during implantation and in throughout a 12 months follow-up period.
	Utility
	 User acceptance of the ARGOS-SC implantation procedure by means of evaluation of implantation procedure questionnaires (investigators)
	- User acceptance of the ARGOS-SC system at the investigational site by means of evaluation of patient acceptance questionnaires (by investigators)
	 User acceptance of the ARGOS-SC system at home by means of evaluation of patient acceptance questionnaires (patients)

Page 12 of 97

	- Daily IOP self-measurement profiles (patients)
	Definition of the analysis populations
	The safety population comprises all subjects for whom ARGOS-SC pressure sensor implantation was attempted, whether or not the implantation was successful. The Per Protocol Set (PPS) will comprise all subjects in whom an ARGOS-SC pressure sensor was successfully implanted and for whom the full data set including IOP measurements made in the clinic and safety data according to protocol are available until 3 months (Visit 6) after surgery.
	Statistical analysis
	Safety analysis
	AEs, SAEs, ADEs and SADEs will be listed and analyzed by descriptive and explorative statistical methods.
	Performance analysis
	The probability distribution of the difference of the paired measurements grouped within 1 mmHg will be compared to the primary objective of the accepted 70% of the measurements to agree between +/- 5 mmHg.
	Interim analysis
	An interim analysis will be conducted to assess safety and performance after the last patient has completed the 6 months follow up visit.
Safety Monitoring	A Data Safety Monitoring Board (DSMB) will be established prior to enrollment of the first patient. The DSMB will review the safety data, including SAEs/SADEs, on a regular basis and will advise on any changes required in the conduct of this clinical investigation.
Data Collection	Data will be collected using a Case Report Form (CRF).
Study Duration	The overall study duration for each individual subject is up to 13 months. Subjects will undergo screening a maximum of 28 days prior to surgery and will be followed for 12 months afterwards.
	The overall recruitment period is expected to last a maximum of 12 months.
	At the start of the study, all patients enrolled in Switzerland will be requested to
	sign up for an additional follow-up of 2 years. These patients will automatically
	transition to the ARGOS-SC_Follow-up.
	The estimated total duration of the study from first patient screened to last patient last visit is 25 months.

TABLE OF CONTENTS

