6.4 Risks and Benefits associated with the participation in the clinical investigation

- ARGOS-SC system associated risks As described in Section 6.2, a full risk analysis was performed during the development of the ARGOS-SC system to anticipate and eliminate or at least minimize all foreseeable ARGOS-SC system-related risks. However as with any new device it is possible that unknown risks remain that will only become apparent as more experience is gained with the device. The safety of the study patients is of paramount importance and will be monitored throughout the study at all times. If at any time a safety issue arises that is thought to be related to the ARGOS-SC implant, to the specific procedures necessary to implant it, or to its use to measure IOP, appropriate measures will be initiated immediately to minimize risk to current and future study patients. All investigators will be kept informed of such issues. The ARGOS-SC was designed to be able to remain in the eye even in the event of failure. If it must be removed, for example due to adverse effects, the risks of removal correspond to those associated with implantation.
- Data Privacy Risks Health data about study patients will be collected and transferred to an electronic database. Although all currently required methods will be used to protect patients' privacy, the security of such databases can never be completely ensured. For this reason, no information that can identify study patients other than the pseudonymising Subject ID will be used on the database or on any study documentation other than the patient log, which will remain at the site. Potential patients will be informed of the data privacy policy during the informed consent process.
- Because of patients' vulnerable nature, there is a risk that they may either feel obligated to participate in the study or that their knowledge of the study may influence their decision whether

or not to undergo NPGS at this time. To mitigate these risks, only patients who have already consented to NPGS will be informed of the study and all potential study patients will be told explicitly that they are free to choose not to participate, and that refusing will not affect their treatment except in regards to the ARGOS-SC system.

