8.3.4 Point of enrollment

A subject is considered as being enrolled into the clinical investigation when he/she gives written consent to participate in this investigation.

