8.3.6 Expected duration of each subject's participation

The maximum duration of each subject's participation in this clinical intervention is 13 months. The point of enrollment is considered to be the time point at which potentially eligible subjects sign the informed consent form. Surgery will be performed within 28 days of enrollment. The subject will be followed-up for 12 months post-surgery to obtain data on safety and performance. At the start of the study, all patients enrolled in Switzerland will be requested to sign up for an additional follow-up of 2 years. These patients will automatically transition to the ARGOS-SC_Follow-up.

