8.3.17 Surgery, Visit 01 (Day 0)

The following procedures may be carried out up to one day before surgery (in subjects already hospitalized for the surgery) or prior to surgery on the day of surgery:

• Verify that the subject continues to meet eligibility criteria

- For female subjects of childbearing potential: collect urine for pregnancy test. A test done within 24 hours prior to surgery must be negative
- Perform external eye photography

The following procedures are to be performed on the day of the surgery:

- Updating medical history (up to start of ARGOS-SC implantation)
- Recording of concomitant medications, device deficiencies or malfunctions (including those detected during device preparation) and any Aes (starting from the point of inclusion/signing of the informed consent)
- Non-penetrating glaucoma surgery and ARGOS-SC pressure sensor implantation (described in Section 8.3.12)
- Completion of the implantation procedure questionnaire (surgeon) and the CRF
- Complete the patient inclusion form and fax it to the sponsor
- Instruct subjects on the need to immediately report any SAE that may occur at any time during the study.
- Schedule Visit 2 (V02).

The duration of the subject's hospitalization following surgery is at the discretion of the Investigator. Durations of up to 6 days will not be considered to be SAEs.

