11.7 Safety Monitoring

A Data Safety Monitoring Board (DSMB) will be established prior to enrollment of the first patient. The DSMB will review the safety data on a regular basis and will advise on any changes required in the conduct of this clinical investigation. The DSMB will consist of 2-4 independent clinicians with expertise in the treatment of glaucoma who are not otherwise involved in the study and will be designated to review safety related issues including reported SAEs/SADEs on a frequent basis and advise the sponsor on any changes required to the conduct of the study. It is anticipated that these clinicians may come to one of three types of binding recommendations, namely:

- 1. Continue the study as planned --No safety issues exist and it is ethical and feasible to continue the study as planned.
- Continue the study with protocol amendments Ethical to continue the study but recommend an amendment to the protocol (e.g. incorporate additional or more frequent safety examinations).
- 3. Stop enrollment and treatment -- Sufficient evidence for a serious safety concern exists, making further implantation of ARGOS-SC pressure sensors in subjects unethical.

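### The automatic pause at each SADE acts on enrollment, formally defined as written consent, so by its terms it does not hold implantations already scheduled

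*Protocol*

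**What the plan says.** The synopsis (Study Design) states: "Enrollment will be halted at every serious adverse device event (SADE". This is the only automatic rule triggered by a SADE. Section 8.3.3.1, on study stopping rules, does not repeat it, and the SAP does not address it.

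Section 8.3.4 defines the term: "A subject is considered as being enrolled into the clinical investigation when he/she gives written consent to participate in this investigation". Section 8.3.6 repeats the definition and adds: "Surgery will be performed within 28 days of enrollment".

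On the step from consent to implantation, the synopsis (Surgery, V01) says "Subjects who continue to meet eligibility requirements will undergo" the glaucoma surgery with sensor implantation. The matching instruction in 8.3.17 is "Verify that the subject continues to meet eligibility criteria". No eligibility criterion in 8.3.1 or 8.3.2 refers to an open SADE.

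Section 11.7 says of the DSMB that "these clinicians may come to one of three types of binding recommendations". The third of these begins "Stop enrollment and treatment". Section 6.4 undertakes that, if a device-related safety issue arises, "appropriate measures will be initiated immediately to minimize risk to current and future study patients".

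**The concern.** In a first-in-human study of a permanent eye implant, an automatic halt is there so that no further eye receives the sensor until a serious device effect has been looked at. The step that creates exposure is implantation. A halt tied to consent acts up to 28 days too early in the pathway: it turns away people who are still weeks from surgery and does not, by its terms, hold those next on the operating list. Sites reading the rule after a SADE would have to choose between the formal definition and what they suppose the sponsor meant. Patient safety is at stake here. No endpoint, analysis or success criterion changes.

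**Working it through.** **Step 1: what the word covers.** The protocol's uses of enrollment point two ways.

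- *Consent is enrollment:* 8.3.4 and 8.3.6, both as formal definitions. Section 9.1.2 tabulates enrolled and implanted subjects as separate counts, and 11.7 names enrollment and treatment as two things to stop.
- *Enrollment comes later:* 8.1.2 enrolls eligible patients after consent and screening. Section 8.3.3.2 describes people who have consented but are not eligible to be enrolled. Section 8.1.5 lets a screen failure occur at any time until the implant is placed. Section 8.3.17 has the inclusion form completed on the day of surgery. Sections 8.3.7 (24 enrolled), 8.2.4 (at most 24 implanted) and 9.5 (24 patients as the denominator) fit together if the enrolled are the implanted.

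The formal definition gives the consent-only reading, and usage is inconsistent with it.

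**Step 2: whether anything else holds a scheduled implantation automatically.**

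| Provision | Reaches waiting patients? | Automatic at a SADE? |
|---|---|---|
| V01 eligibility re-check (synopsis, 8.3.17) | Yes | No; no criterion mentions a SADE |
| 6.4, immediate measures | Yes | No; measures not specified |
| 11.7 and 9.7, DSMB | Yes | No; needs a DSMB conclusion |
| 12.1, inform and if necessary re-consent on new safety information | Yes | No; needs a judgement of relevance |
| 12.8, immediate investigator action | Yes | No; investigator's judgement |
| 8.3.3.1 and 12.11, sponsor suspension | Yes | No; sponsor's decision |

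**Step 3: scale.** The plan gives no figure to reproduce. Inputs are 24 implants (8.2.4), at most 12 months of recruitment (8.3.7) and at most 28 days from consent to surgery (8.3.6). With implantations evenly spread (an assumption):

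consented patients waiting, on average = implantation rate × wait

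12 months: 24/365 = 0.066 per day, and 24/365 × 28 = 1.84.

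| Recruitment | 7-day wait | 14-day wait | 28-day wait |
|---|---|---|---|
| 12 months (plan's maximum) | 0.46 | 0.92 | 1.84 |
| 9 months (assumed) | 0.61 | 1.23 | 2.45 |
| 6 months (assumed) | 0.92 | 1.84 | 3.68 |

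The 7- and 14-day waits are also assumed. Treating the number waiting as Poisson, the chance that at least one patient is waiting is 1 − e^(−1.84) = 0.84 at 12 months and 28 days, 0.37 at 12 months and 7 days, and 0.98 at 6 months and 28 days.

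The documents set no time for reviewing a single SADE. If a review took an assumed 3 to 7 days and patients had consented at least that long before surgery, then at the 12-month rate 24/365 × 3 = 0.20 to 24/365 × 7 = 0.46 implantations would fall inside it.

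**The case against.** The strongest reply is that the protocol in practice treats a patient as enrolled only once screened and operated on, as the later uses in step 1 show. On that usage, halting enrollment does halt implantation. This stands in part: the sponsor may well have meant it. It does not remove the point, because the one explicit definition, given twice, says otherwise, and 9.1.2 and 11.7 keep the steps apart. The contrast with 11.7 should not be pressed far. That option is a DSMB stop on sufficient evidence, so its different wording does not show that the synopsis rule deliberately left implantation out.

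The second reply is that waiting patients are already protected. They are current study patients under 6.4, they must be told of relevant new safety information under 12.1, and 12.8 expects the investigator to act at once even against the plan. The site reports SAEs to the sponsor immediately (11.4), and the sponsor knows of scheduled surgeries (8.3.16). All of this stands. A reader might infer that the plan lets implantation carry on regardless after a SADE, or that a surgeon would be obliged to implant. The documents do not support either. What is missing is narrower: none of these provisions makes the scheduled implantation wait without a separate decision.

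The third reply is that the numbers are small and partly assumed. That is correct. Section 9.5 also allows a successful study at most one patient with SADEs, so few such pauses would arise in one.

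**Conclusion.** The point holds as a conflict between a formal definition and the evident purpose of the halt. By the definition in 8.3.4 and 8.3.6, the automatic rule does not hold scheduled implantations of consented patients, and only discretionary safeguards cover them.

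About 1.8 consented patients would be waiting on average at a SADE during recruitment, given 24 implants evenly spread over 12 months and a 28-day wait. It might be tempting to read 1.8 as a ceiling. It is not, because 12 months is the longest recruitment expected, so 24/365 is the lowest average rate if all 24 are implanted. Shorter waits lower the figure (0.9 at 14 days, 0.5 at 7) and faster recruitment raises it (3.7 at 6 months and 28 days). It is zero for a SADE after the last implantation. Nor does it measure harm: it counts implantations that the automatic rule leaves unheld, before any action under the other provisions. The weight is low. This is a cheap improvement to patient safety.

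**What to change.** Amend the synopsis sentence and add the same rule to 8.3.3.1:

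> Each SADE pauses new consents and all scheduled ARGOS-SC implantations at every site until the DSMB has reviewed the event and recommended continuation; the indicated glaucoma surgery may go ahead without the sensor, and such a subject is replaced under 8.1.5 and 8.3.3.3.

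Sections 6.4, 9.7 and 11.7 can stay as they are.

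The cost is one sentence in two places, handled as a protocol amendment under 12.4 and 12.8. The pause in consents is already planned, so the added burden is a few implantations postponed or forgone per SADE: 0.2 to 0.5 for an assumed 3 to 7 day review at the 12-month rate, and more with faster recruitment or a longer review. A patient whose surgery moves beyond 28 days from consent would need fresh consent and screening. Glaucoma care need not be delayed, since 8.3.1 requires the surgery to be indicated irrespective of the study, and replacement of patients not implanted is already provided for.
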